Beginning at the baseline visit (in person) and continuing daily throughout the intervention (online), participants will be asked to complete a child-adapted version of the validated Caffeine Withdrawal Symptoms Questionnaire (CWSQ). During the baseline visit, child participants will taste a small sample of each study beverage in pairs and will rate which beverage they like better and which beverage tastes sweeter using the enclosed beverage taste testing form. Child participants will be randomized into one of three study arms, where they will be instructed to replace their usual caffeinated SSBs with either: caffeinated SSB's provided by the study team, caffeine-free SSBs (caffeine-free Pepsi) or unsweetened sparkling water (LaCroix), compared to control (regular Pepsi consumption) for two weeks. All beverages will be provided by the study team, including drinks for the control group. After randomization, participants (child and parent together) will complete a daily online compliance questionnaire.

An outline of the schedule of study activities is below:

Time	Activity
Baseline Study Visit (Day 0) 1.5 hours	
 • Consent/assent • Height and weight • Complete in-person Caffeine Withdrawal Symptoms Questionnaire (CWSQ) with parent and child [this is called Daily Feelings Questionnaire in the Assent Form for kid-friendly language] • Dietary recall (parent and child)

	
 • Beverage taste testing (child) • Randomization and counseling regarding intervention (parent and child) • Provision of study beverages

Intervention (Days 1-14) Total of 1 hour per week
	
 • Parents receive three times weekly text message/email/phone reminders (based on participant preference) from study team • Parent and child together complete daily online CWSQ • Parent and child together complete daily online compliance survey • Child participant consumes assigned study beverages

Mid-intervention Visit Or Telephone Check-in (after first week of intervention)
 
~30-45 minutes
	
 • Complete in-person Caffeine Withdrawal Symptoms Questionnaire (CWSQ, parent and child together) • Dietary recall (parent and child together) • Provision of additional study beverages if needed • Participants and their parents encouraged to ask questions or express concerns

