
Follow-up visit (Day 15) 1.5-2 hours
	
 • Complete in-person Caffeine Withdrawal Symptoms Questionnaire (CWSQ, parent and child together) • Dietary recall (parent and child together) • Beverage taste testing (child participant) • Return empty study beverages • Qualitative interview (~20 minutes, parent and child together)

Details of all study procedures are described below:

Study Procedure	Description
Height and weight	Child participant's height and weight will be measured using a portable scale and stadiometer.
Caffeine Withdrawal Symptoms Questionnaire (CWSQ)	Parent and child participants will together complete a child-adapted version of the validated CWSQ ⁸ in person at baseline, and online daily throughout the intervention. [name] and/or a trained RA will assist with CWSQ completion at baseline and will counsel participants regarding filling out the online questionnaire.
24 hour dietary recalls	Participants will be asked (with the help of their parent) to report everything that they eat and drink over the past 24 hours. 24-hour recalls will be conducted at baseline (in person), after 1 week of the intervention (in person or via phone depending on participant preference), and at follow-up (in person).
Beverage taste testing	Prior to randomization, child participants will taste pairs each study beverage (10 mL) in randomized order and rate which beverage they like better and which beverage tastes sweeter using the taste enclosed taste testing form. Participants will rinse with water between each test. Taste testing will be completed in a private room and supervised by trained RAs. Child participants will also complete taste testing at follow-up.
Compliance questionnaires	Participants (child and their parent) will complete an online, 4-item questionnaire daily throughout the intervention to assess compliance (percentage of assigned beverages consumed, assessment of whether caffeinated SSB were consumed in violation of the study protocol, and if so, the brand and quantity consumed).
Randomization and Blinding	Following baseline assessments, child participants will be randomized using sex-stratified permuted block randomization into one of three arms: 1) caffeine-free SSBs (caffeine-free Pepsi) 2) unsweetened sparkling water (LaCroix) or 3) control (Pepsi).

	Assigned beverages will replace usual caffeinated SSB consumption, as assessed at enrollment.

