Beverage distribution	A two-week supply of beverages (corresponding to randomization and the amount of SSBs typically consumed) will be provided. If a participant runs out of beverages, the study team will provide additional beverages. Children will be counseled to drink only the study drinks provided or water and not to consume any other beverages during the two week intervention. Parents will also be counseled regarding encouraging their child to consume only the study beverages or water throughout the two week study period.
Compliance and reminders	Compliance will be assessed by collection of empty beverage containers. Empty containers will be picked up by the study team at the end of the intervention to minimize participant burden. If a participant is provided with additional beverages, empty containers will be requested prior to distribution of more beverages. Compliance will be further monitored during dietary recalls.
Mitigation of withdrawal symptoms	If a child experiences headaches, nausea, or other discomfort, they will be asked to report symptoms using the CWSQ before taking pain or anti-nausea remedies. Children and their parents will be discouraged from using over-the-counter medications, unless the severity of the symptoms are reported to be above a pre-determined threshold (rating of 4 or higher on the CWSQ Likert scale). In addition, participants will be strictly instructed not to use any pain remedy containing caffeine.

Data analysis:

Caffeine withdrawal scores will be collected using the CWSQ, completed by the child and parent together. Peak withdrawal symptoms will be operationalized as CWSQ scores reported within the initial 72 hours of the intervention, between the three groups. Univariate analyses and one-way ANOVA will be used to assess group differences in our primary (measures of compliance with beverage intervention) and secondary (withdrawal symptoms) study outcomes.

Dietary recalls will allow us to assess adherence to the study beverages as replacements for habitual caffeinated SSBs and to determine if caffeinated SSB removal impacts dietary choices. While we acknowledge limitations inherent to self-report dietary assessment, dietary recalls are sufficient for capturing beverage consumption data and will enable us to determine whether participants change their diet to compensate for caffeine restriction.

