Compliance with beverage consumption will be assessed using beverage/compliance logs (completed by the parent and child together). We will operationalize compliance as the number of days in which participants consumed the study beverages, the total number of study beverages consumed during the intervention period, as well as any consumption of caffeinated SSB, juices etc. (in violation of the study protocol). Importantly, participants are being instructed simply to consume the study beverages in the same manner that they would normally consume their usual caffeinated sugar-sweetened beverages. They will not be assigned to consume a certain number of study beverages, but instead instructed to replace their usual beverages with the study drinks or water throughout the intervention period.

Liking of study drinks may affect compliance and we will therefore run exploratory multivariable linear regression models including taste ratings as a potential confounder, along other potential covariates such as sex, race/ethnicity, age, weight, and volume of habitual SSB consumption. While we recognize that we are not sufficiently powered for multivariable regression models including a large number of covariates, these data will be critical in informing sample size calculations for our subsequent R01 proposal. We will use an intention to treat (ITT) approach and will minimize loss to follow-up by maintaining close contact with participants. All analyses will be conducted using SAS 9.4.

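### The one-way ANOVA planned for withdrawal symptoms leaves out the Day 0 CWSQ taken before randomization; the test is valid but may give up precision that the data could supply

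*Protocol*

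**What the plan says.** The test is stated in the protocol, section D, Data analysis, and repeated in the SAP under Statistical Design and Power: "Univariate analyses and one-way ANOVA will be used to assess group differences in our primary" outcome (compliance) and in the secondary outcome (withdrawal symptoms). The withdrawal measure is set out just before it: "Peak withdrawal symptoms will be operationalized as CWSQ scores reported within the initial 72 hours of the intervention, between the three groups". It is not defined as a change from baseline, and no baseline term appears.

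The baseline score is nevertheless collected. The schedule of study activities lists, for the Day 0 visit, "Complete in-person Caffeine Withdrawal Symptoms Questionnaire (CWSQ) with parent and child". The Randomization and Blinding entry of the procedures table fixes the order: "Following baseline assessments, child participants will be randomized using sex-stratified permuted block randomization into one of three arms". The Day 0 CWSQ is therefore a pre-randomization measurement, and sex is the stratification factor.

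The only adjusted models are exploratory. They are introduced because liking of the drinks may affect compliance, and they include taste ratings "along other potential covariates such as sex, race/ethnicity, age, weight, and volume of habitual SSB consumption". Baseline CWSQ is not named there. The list is open-ended and the univariate analyses are not defined, so the baseline score is unstated rather than excluded.

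**The concern.** Withdrawal is Aim 2. With 20 children per arm and no adjustment, a pairwise arm difference has a 95% CI of about ±0.63 SD, which is wide. A baseline measurement of the outcome is usually the first candidate for a covariate. Here it is already scheduled, precedes randomization and costs almost nothing to use. If children who score high on Day 0 also tend to score high in the first 72 hours, the ANOVA leaves that predictable variation in its error term.

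The open covariate list adds a smaller point. With no adjusted analysis of withdrawal specified, adjusted and unadjusted results could both be produced and one preferred after the data are seen.

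**Working it through.** **The plan's own figure.** No power calculation is given to reproduce. The SAP states 60 children at 20 per group, and 3 × 20 = 60 agrees.

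**Inputs from the documents.** Three arms, n = 20 each; Day 0 CWSQ before randomization; stratification by sex.

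**Assumptions, because the documents are silent.** Two-sided alpha 0.05; normal outcomes; complete data on all 60 children; effects in SD units; r = 0.3, 0.5 or 0.7 between the Day 0 and 72-hour values; sex balanced within arm, explaining no variance and costing one degree of freedom.

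**Degrees of freedom.** ANOVA: 60 − 3 = 57. ANCOVA with Day 0 CWSQ and sex: 60 − 3 − 2 = 55.

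**Variance factor.** The variance of an arm contrast, relative to ANOVA, is (1 − r²) × 56/55. The second term is the price of chance baseline imbalance. At r = 0.5: 0.75 × 1.018 = 0.764.

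**Equivalent sample size.** 20 / factor. At r = 0.5: 20 / 0.764 = 26.2 per arm.

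**Half-width of the pairwise 95% CI.** t × √(2/20) × √factor. ANOVA: 2.002 × 0.316 = 0.633 SD. ANCOVA at r = 0.5: 2.004 × 0.316 × 0.874 = 0.554 SD.

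**Power.** Non-central F on 2 and 57 (ANOVA) or 55 (ANCOVA) degrees of freedom. With both removal arms shifted by d, the arm means are 0, d, d, so the non-centrality is 20 × (4/9 + 1/9 + 1/9) × d² = 13.33 d², divided by the factor for ANCOVA. For d = 0.8 under ANOVA it is 8.53.

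| Analysis | Variance factor | Equivalent n per arm | CI half-width (SD) | Power, d = 0.8 | Power, d = 0.5 |
|---|---|---|---|---|---|
| ANOVA | 1 | 20 | 0.633 | 72.3% | 33.7% |
| ANCOVA, r = 0 | 1.018 | 19.6 | 0.639 | 71.4% | 33.1% |
| ANCOVA, r = 0.3 | 0.927 | 21.6 | 0.610 | 75.7% | 36.0% |
| ANCOVA, r = 0.5 | 0.764 | 26.2 | 0.554 | 83.8% | 42.8% |
| ANCOVA, r = 0.7 | 0.519 | 38.5 | 0.457 | 95.1% | 59.0% |

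**Break-even.** The factor equals 1 when r² = 1/56, so r = 0.134.

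**Validity.** In 20,000 simulated trials with no effect, both methods rejected 4.7 to 5.1% of the time. Simulated ANCOVA power at d = 0.8 was 75.3, 83.5 and 95.0%, in line with the table.

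**Does the gain depend on how 72 hours of scores become one value?** Take the 72 hours as Days 1 to 3, all pairwise correlations among Day 0 and those days as 0.3, 0.5 or 0.7, and a 0.5 SD shift on each day (8,000 simulated trials per setting, complete diaries). For the mean of the three days, power rises from 58, 48 and 42% to 66, 69 and 81%. For the highest score it rises from 46, 42 and 39% to 52, 58 and 72%. Adjustment helps with either summary.

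**Floor effects.** CWSQ items start at 0. If scores are censored so that about 69% of Day 0 values sit at the floor (an assumed figure), power for a 0.8 SD latent shift is about 50% with ANOVA, against about 52, 57 and 69% with ANCOVA at latent r = 0.3, 0.5 and 0.7. With about 84% at the floor it is about 33%, against about 32, 35 and 43%. The gain shrinks and, at low r, vanishes.

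**The case against.** The strongest reply is that nothing here is wrong. ANOVA on one value per child is unbiased under randomization and holds its level. Withdrawal is secondary, Aim 2 is exploratory, and both documents say that sample size was not calculated for clinical outcomes. This stands, and it sets the severity.

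The second reply is that r may be low. The form in the protocol appendix asks how the child feels at that moment. Setting differs too: "a trained RA will assist with CWSQ completion at baseline and will counsel participants regarding filling out the online questionnaire", so Day 0 is completed in person with help and the daily scores online. At r = 0.3 the gain is 1.6 children per arm and 2 to 3 points of power, and the table assumes normal, complete data. This also stands: the r = 0.7 row is a possibility that nothing in the documents supports. What remains is the asymmetry: at d = 0.8 about 1 point of power is at risk if r = 0, against about 12 points gained at r = 0.5.

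Three stronger readings are tempting, and the documents do not support them.

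- A reader might infer that the trial needs ANCOVA to plan its successor, because the authors say that "these data will be critical in informing sample size calculations for our subsequent R01 proposal". But the baseline correlation and residual SD can be calculated from the collected data whichever test is prespecified, and that sentence concerns the exploratory regression models.
- A reader might infer that the plan rules out baseline adjustment. It does not; the covariate list is open.
- A reader might infer that the 72-hour value should be the mean of the daily scores, or that a maximum should be limited to children with complete diaries. The documents name a peak construct, so moving to the mean changes what is estimated. It is also a trade-off: if a 0.8 SD shift falls on one day only, the highest score has power of 31, 39 and 57%, against 23, 24 and 30% for the mean. Limiting the analysis to complete diaries conditions on behaviour after randomization, which fits badly with the stated intention-to-treat approach.

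The documents also leave open how several scores become one value, how items are scored, and how to treat symptom-triggered reports (children with discomfort are told that "they will be asked to report symptoms using the CWSQ before taking pain or anti-nausea remedies"). Those are separate gaps that affect any test, and they add no weight to this point.

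**Conclusion.** The point holds as a matter of efficiency only. The stated test of withdrawal is valid but does not use a pre-randomization measurement of the same outcome. At moderate correlation (r = 0.5) adjustment is worth about 6 extra children per arm (26.2 against 20); at r = 0.3 it is worth fewer than 2, and below about 0.13 nothing. The worst case in the table, r = 0, costs about 2% of variance and 1 point of power. These sizes rest on an assumed r, normal outcomes, full data on 20 per arm and two-sided alpha 0.05, and would be smaller with many scores at the floor. For a secondary outcome in a feasibility pilot this is a low-severity improvement worth making, not a correction of an error.

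**What to change.** In the SAP, and in the matching protocol paragraph, replace the one-way ANOVA for withdrawal with an ANCOVA of the chosen 72-hour CWSQ value on arm, Day 0 CWSQ and sex. Score Day 0 and the 72-hour value by the same rule. Report arm differences with 95% CIs, together with the baseline correlation and the residual SD. Keep the peak construct as the documents name it; the change works with whichever single 72-hour value is chosen. Settle the wording before any analysis by arm.

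The cost is a few sentences of SAP text, a few lines of SAS and two of the 57 error degrees of freedom. No new data, visits or participants are needed.

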RESEARCH PROTOCOL

Required Elements

TITLE: Investigating withdrawal symptoms as barriers to reducing sugar-sweetened beverage consumption among children: pilot intervention study

IRB #: NCR191271

VERSION DATE: June 3rd, 2019

RESEARCH PLAN

A. **Specific Aims**

Specific Aims and Hypotheses:

1. Examine the feasibility of removing caffeinated sugar-sweetened beverages (SSB) from the child diet. We hypothesize that caffeinated SSB avoidance will be feasible among children, but that compliance will be lowest among those assigned to sparkling water, devoid of both caffeine and sugar. Compliance with beverage assignments will be assessed using daily online questionnaires and weekly dietary recalls.
2. Explore the extent to which caffeinated SSB removal induces withdrawal symptoms. We hypothesize that replacement of caffeinated SSBs with caffeine-free SSBs, or sparkling water will induce withdrawal symptoms compared to control (usual caffeinated SSB consumption). Participants will complete a child-adapted version of the validated Caffeine Withdrawal Symptoms Questionnaire (CWSQ) at baseline and daily (online) during the intervention.

B. **Background and Significance**

Sugar-sweetened beverages (SSBs) significantly contribute to sugar and calorie intakes, and their consumption is associated with metabolic disease.¹ Sweetened beverages also account for the majority of pediatric caffeine consumption.² It is well-established that habitual caffeine use leads to dependence in adults³ and evidence for sugar dependence has been documented.⁴ However, caffeine and/or sugar dependence related to sweetened beverage consumption has not been evaluated, and determinants of their consumption among youth are severely understudied. It is critical to elucidate whether they may be physiologically or psychologically dependent on these beverages, particularly SSBs, which contain both caffeine and sugar.

The purpose of this pilot study is to replace caffeinated SSB's with either caffeinated SSBs provided by the study team (control) or with caffeine-free and unsweetened alternatives (also provided by the study team) for 2 weeks, among children who habitually consume caffeinated SSBs.

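### The primary outcome is three unranked compliance measures: two count uptake of the supplied drink, and none isolates the removal of caffeinated SSBs that Aim 1 asks about

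*Protocol*

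**What the plan says.** Protocol section A gives Aim 1 as "Examine the feasibility of removing caffeinated sugar-sweetened beverages (SSB) from the child diet" and expects that "compliance will be lowest among those assigned to sparkling water, devoid of both caffeine and sugar". It says compliance with the assignment will be assessed by daily questionnaires and weekly dietary recalls.

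Protocol section D (Data analysis) and the SAP (Statistical Design and Power) name the primary outcome only as measures of compliance, in the plural. Both use the same three parts: "We will operationalize compliance as the number of days in which participants consumed the study beverages, the total number of study beverages consumed", and then "any consumption of caffeinated SSB, juices etc. (in violation of the study protocol". Neither document ranks or combines them, or sets a feasibility threshold.

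The Data analysis text also says that no number of study drinks is assigned and that children are "instructed to replace their usual beverages with the study drinks or water throughout the intervention period". The Beverage distribution row agrees: "Children will be counseled to drink only the study drinks provided or water and not to consume any other beverages".

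The Compliance questionnaires row says the daily form covers the share of assigned drinks taken, without stating a denominator, and "assessment of whether caffeinated SSB were consumed in violation of the study protocol, and if so, the brand and quantity consumed". In the appendix form, item 2 asks about other sugary drinks and item 4 about caffeinated drinks such as coffee or tea; both record brand and quantity. Empty containers and 24-hour recalls are further adherence sources. Adjustment for habitual intake appears only in exploratory models with taste ratings, "along other potential covariates such as sex, race/ethnicity, age, weight, and volume of habitual SSB consumption".

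**The concern.** Uptake of a supplied drink and avoidance of caffeinated SSBs are different quantities, and under this protocol's rules they can move in opposite directions. If more children in the sparkling-water arm turn to plain water, both uptake measures fall there while avoidance may be the same in all arms. Both results would be true, but they answer different questions. The plan does not say which one answers Aim 1, so the feasibility message could rest on a choice made after the data are seen. Feasibility is the study's stated primary purpose, and its data are meant to inform a larger proposal.

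A secondary issue is that the raw total of study drinks also reflects how much soda each child drank before the study. That adds noise to the comparison between arms.

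**Working it through.** **Plan's own figure.** 3 arms × 20 = 60, as the SAP states. Neither document gives an alpha, power, effect size or uptake rate. The 5% level and every rate below are assumptions.

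**Scoring three children under the written rules (either caffeine-free arm, 14 days).**

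| Child | Study-drink days | Study drinks | Off-protocol drink | Caffeinated SSB removed? |
|---|---|---|---|---|
| Replaces all soda with water | 0 | 0 | none | yes |
| Study drink daily, keeps usual soda | 14 | 14 or more | yes | no |
| Study drink daily, plus juice | 14 | 14 or more | yes | yes |

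The first two rows show uptake ordering children opposite to removal. The last two show that the third measure, as pooled, cannot separate a child who removed caffeinated SSB from one who did not. In the control arm the study drink is itself a caffeinated SSB, so uptake there is not removal at all.

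**Other sources.** Recalls are at baseline, after week 1 and at follow-up. Those after baseline cover about 2 of the 14 intervention days. Empty containers show use of supplied drinks, not of other drinks.

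**When uptake differs although avoidance does not.** 20,000 simulated trials per scenario, 20 per arm, one-way ANOVA at 5%, no violations in any arm, 90% uptake in the two Pepsi arms. Habit h is 1, 2 or 3 cans a day in 50, 30 and 20% of children. Child uptake p is beta-distributed with SD 0.20; days ~ Binomial(14, 1−(1−p)^h); totals ~ Binomial(14h, p).

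| Sparkling-water uptake | Days significant | Totals significant |
|---|---|---|
| 85% | 7% | 6% |
| 80% | 19% | 10% |
| 70% | 57% | 27% |
| 50% | 99% | 89% |

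Equal 90% uptake in all arms gives about 4 to 5%. If instead every child has h = 2 and p does not vary within an arm, the figures are 21% (days) and 73% (totals) at 85%, and 70% and 100% at 80%. The model decides even which uptake measure is more sensitive.

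**Habit noise in the raw total.** Total = 14 × habit × uptake; habit lognormal; uptake 85/85/65% by arm with SD 20 points. Analytic check for the total scaled to true habit: deviations from the mean of 78.33 are 6.67, 6.67 and −13.33, with squares summing to 266.7. The noncentrality is 20 × 266.7/20² = 13.33, which on F(2, 57) gives 90.0% power.

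| Approximate power at habit CV | 0.25 | 0.33 | 0.50 |
|---|---|---|---|
| Raw total | 62% | 48% | 28% |
| Habit as only covariate | 87% | 86% | 82% |
| Covariate, 25% baseline error | 73% | 67% | 58% |
| Covariate, 35% baseline error | 68% | 61% | 49% |

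Scaling to measured baseline gives 61–62% with 25% error and about 45% with 35% error. The latter is below the raw total at CV 0.25 and 0.33. The covariate is therefore the safer adjustment.

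**Missing diaries under the proposed measure.** A child with 2 clean diaries and 12 missing scores 100% on completed days and 2/14 = 14% with missing days counted as not avoided. With true avoidance 90% and 10% of diaries missing at random, the two versions give 90% and 0.90 × 0.90 = 81%. With true avoidance 70%, completion 90% on clean days and 45% on violation days, completed days give 0.63/(0.63 + 0.135) = 82% and the 14-day version gives 63%. These bracket the truth.

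**Precision.** The 95% CI half-width for an arm mean is 2.093 × SD/√20 = 4.7, 9.4 or 14.0 points for an assumed between-child SD of 10, 20 or 30 points.

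**The case against.** The best defence is that this is a 60-child pilot with no stated alpha and no sample size calculation for clinical outcomes. Reporting several feasibility measures side by side is normal there. Aim 1's own wording points to compliance with the assignment, which uptake measures, and low uptake of sparkling water would fit the stated hypothesis. This stands: uptake belongs in the report, and the remaining risk is selective emphasis.

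A reader might infer that removal is not measured at all. The documents do not support that. The third measure bears on it, item 2 of the daily form can identify a caffeinated soda by brand, and both documents use the recalls to assess study drinks as replacements for habitual caffeinated SSBs. What is missing is a coding rule and a named lead measure.

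A reader might also infer that the instructions on water contradict each other. That is too strong. The Beverage distribution row, the Data analysis text and the SAP all allow water, and the Randomization row does not forbid it. The differences are small: the reminder message omits water, and the SAP names only study drinks as the replacement while allowing water to be drunk.

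Finally, the simulations show true differences in uptake under assumed rates. They do not show that the trial would reach a wrong conclusion.

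**Conclusion.** The point holds in limited form. Followed as written, the plan yields three unranked results, none of which isolates removal of caffeinated SSBs, so the answer to Aim 1 can turn on which is stressed. The logic needs no assumed rate; the size does. In the main model a 5-point drop in sparkling-water uptake has a negligible effect on the days and totals tests, and a large effect needs a clear difference between arms in swapping to water. The gain from adjusting volume for baseline habit is substantial in the scenarios tried, but shrinks as baseline error grows.

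It would be tempting to add an inflated error rate: three independent tests at 5% give 1 − 0.95³ = 14.3%. The plan states no alpha and makes no confirmatory claim, so that figure is only illustrative. Lower severity is appropriate for a pilot, although the change is cheap and worth making.

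**What to change.** In the protocol's Data analysis text and in the SAP:

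1. Name as the lead Aim 1 measure the per-child proportion of intervention days with no non-study caffeinated SSB, coded from brand and quantity in items 2 and 4 of the daily form, each day counted once. Report it per arm with a 95% CI over completed diary days. Add a sensitivity version over 14 days that includes every randomised child and counts missing days as not avoided. Cross-check against the dietary recalls. Report juice and other drinks separately. In the control arm call it avoidance of non-study caffeinated SSB; describe removal only for the two caffeine-free arms; and state that the three-arm ANOVA compares avoidance of non-study drinks.
2. Keep study-drink days and volume as separately labelled uptake measures. Compare volume between arms with baseline habitual caffeinated-SSB volume as the single covariate, and show percentage of baseline descriptively only.
3. Reconcile the reminder message and the SAP wording on water with the Beverage distribution and Data analysis text, so that uptake scoring matches the instruction given. Which wording applies is for the investigators to decide.

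The cost is wording, brand coding and analysis; the data are already planned. The downsides are self-report, a possible ceiling on avoidance, and coarse baseline volume categories with an open top. The 14-day version is a lower bound for missing diaries only, not for under-reporting.
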